A number of quantitative and semi-quantitative imaging biomarkers for each tracer will be computed at each imaging time point, and the change in each biomarker between time-points will also be computed. These data will be compared with clinical endpoints (standard RANO criteria, survival, time to progression), and with tumor biologic information (histology, WHO grade, vascularity, MIB-1, VEGF, EGFR, p53, IDH status) in cases when tumor tissue becomes available from standard care. These preliminary and exploratory data will provide information regarding semi-quantitative changes in uptake consistent with standard response, the potential value of concurrent multiple PET biomarkers for predicting tumor behavior prior to the start of therapy, for improved prognostication, for more efficient and effective tumor surveillance, and/or for more appropriate assignment of patients to conventional, aggressive, or investigational therapies early in their clinical courses. This initial data will be important for design of subsequent clinical trials using [F]Fluciclovine and/or [F]FLT to assess response to chemoradiation in high-grade primary brain tumor.

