## 2. BACKGROUND

### 2.1. Malignant Brain Tumors

Despite significant advances in the understanding of brain tumor biology and genetics as well as improvements in surgical techniques, radiotherapy administration, and chemotherapy methods; most primary brain tumors remain incurable. Most primary brain tumors are highly infiltrative neoplasms, and are therefore unlikely to be cured by local treatments such as surgery, focal radiotherapy, radiosurgery, or brachytherapy.

The clinical presentation of a brain tumor is highly dependent on its location within the nervous system; but includes signs/symptoms that relate directly to compression and/or infiltration of specific functional areas of brain parenchyma, increased intracranial pressure, hydrocephalus, cerebral edema, and/or vascular complications from the tumor. The most common symptoms include headaches, cognitive deficits, nausea/vomiting, seizures, balance disturbances, and focal neurologic deficits. Once clinically suspected of having such a lesion, a patient usually undergoes an imaging procedure, typically a computed tomography (CT) scan or a magnetic resonance (MR) scan. Neurosurgical intervention, in the form of either a brain biopsy or craniotomy with resection, is the next step to obtain a tissue diagnosis and, if warranted, to decrease the tumor mass.

There are approximately 16,900 new cases of primary CNS tumors diagnosed in the United States each year. Numerous studies have documented an increase in the incidence of these tumors in the last decades (Sanson-Fisher et al., 2000). About 50% of these lesions are supratentorial high-grade gliomas. Anaplastic astrocytoma (AA) (WHO Grade III) and glioblastoma (GBM) (WHO Grade IV) are the most common glial primary brain tumors with at least 80% of malignant gliomas being GBMs (Brock et al., 1998, Ichimura et al., 1998). Patients with newly diagnosed malignant gliomas are usually treated with biopsy or surgical resection followed by radiation therapy and/or chemotherapy; depending on their functional status. Despite these interventions, the median survivals for newly diagnosed GBM and AA are 50 and 150 weeks, respectively. Chemotherapy has been shown to increase the proportion of long-term survivors from less than 5% to between 15-20 % (Treat et al., 2012). Once a patient has failed initial therapy, salvage therapy is difficult and most patients die of tumor progression within 4-12 months (Group, 2002).

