To date there have been no human studies assessing the use of [F]FLT to assess response to chemoradiation in primary high-grade brain tumors. Several studies have been performed assessing brain tumor treatment response in patients receiving chemotherapy and/or bevacizumab (Chen et al., 2007, Schwarzenberg et al., 2012, Wardak et al., 2014). A single study by Chen (Chen et al., 2007) used [F]FLT to predict response in malignant glioma in patients receiving Bevacizumab and Irinotecan as second line therapy. The patients were treated with biweekly cycles of bevacizumab and irinotecan and were prospectively studied with [F]FLT-PET at baseline, after 1 to 2 weeks, and after 6 weeks from start of treatment. A more than 25% reduction in tumor [F]FLT uptake as measured by standardized uptake value was defined as a metabolic response. In this study there were nine responders (47%) and 10 non-responders (53%). Responders survived three times as long as non-responders (10.8 v 3.4 months;  $P = .003$ ), and tended to have a prolonged progression-free survival ( $P = .061$ ). Both early and later [F]FLT -PET responses were more significant predictors of overall survival (1 to 2 weeks,  $P = .006$ ; 6 weeks,  $P = .002$ ), compared with the MRI responses ( $P = .060$  for both 6-week and best responses). A second study was published as an extension of the Chen study assessing response using [F]FLT and [F]FDOPA. This study showed the superiority of using kinetic modelling and multiple linear regression analysis to improve the predictive ability of the radiopharmaceuticals. Kinetic parameters from FLT were more predictive of overall survival than those from FDOPA. Using information from both radiopharmaceuticals resulted in a better three predictor model (adjusted R^2 = 0.83) than using information from FDOPA alone (adjusted R^2 = 0.41), and only marginally different from using information from FLT alone (adjusted R^2 = 0.82). Another study by Schwarzenberg (Schwarzenberg et al, 2012) assessed early survival prediction in patients receiving bevacizumab chemotherapy. In this study early and late changes in tumor [F]F-FLT uptake were more predictive of overall survival than MRI criteria ( $P < 0.001$  and  $P = 0.01$ , respectively). [F]F-FLT uptake changes were also predictive of progression-free survival ( $P < 0.001$ ). The median overall survival for responders was 3.3 times longer than for non-responders based on [F]F-FLT PET criteria (12.5 vs. 3.8 months,  $P < 0.001$ ). A potential limitation of these studies was the use of standardized uptake value rather than full kinetic analysis in brain tumors (Peck et al., 2015). This is due to the fact that [F]FLT is restricted at the blood-brain-barrier. This results in a transport-dominated SUV image because transport of [F]FLT is the rate-limiting path to uptake. Studies utilizing full kinetic analysis would be helpful to test whether there

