## 5. TRIAL DESIGN

### 5.1. Patient Eligibility

Two different groups of patients will be able to enroll in the trial. The first group, Group A, will be for patients who have not yet received any therapy for their suspected or newly found brain tumors. Group B will enroll patients with pathologically proven malignant brain tumor (WHO Grade III or IV glial-based tumors) who have undergone chemoradiation and have a contrast enhancing mass ≥ 1.0 cm in greatest diameter concerning for pseudoprogression. MRI-documented possible recurrence/progression versus treatment effect (pseudoprogression) within 6 months from the time of completion of chemoradiation.

Group A will have three different patient cohorts. The first, for patients where there is compelling evidence, based on the MRI and/or CT imaging, that a high-grade primary brain tumor is present. Pathologic confirmation will occur with subsequent biopsy or surgery. The second cohort of patients are individuals where the tumor is felt to be inoperable and a biopsy is performed but no surgery. The third cohort of patients are post-surgery where a complete surgical resection was not possible. This will be confirmed by a post-operative contrast MRI/CT scan where residual tumor  $\geq 1.0$  cm in diameter is present.

Eight to ten patients per year will be enrolled, for a total of 30 patients. Providers within the Radiation Oncology and Neuro-Oncology departments will identify and recruit patients who may be eligible participants.

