#### Primary Endpoint

The primary endpoint of the study is that a 25% reduction in  $SUV_{max}$  or  $SUV_{mean}$  for each of the PET imaging tracers will be predictive of increased overall survival. These endpoints will be analyzed by

Kaplan-Meier analysis and logrank tests. Cox proportional hazards regression will also be used to estimate hazard ratios. Each analysis will be performed at the two sided 0.0125 significance level to adjust for four comparisons.

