With an initial sample size of 30, we estimate that approximately 75% of the subjects (N = 22) will have both a [F]Fluciclovine-PET and [F]FLT-PET after completion of initial chemoradiotherapy. Our justification of sample size is based on data on the prediction of OS using PET reported in Chen et al. (Chen et al., 2007). In this study more than 25% reduction in tumor [F]FLT uptake as measured by standardized uptake value was defined as a metabolic response. In this study there were nine responders (47%) and 10 non-responders (53%). Responders survived three times as long as non-responders (10.8 v 3.4 months;  $P = .003$ ), and tended to have a prolonged progression-free survival ( $P = .061$ ). Both early and later [F]FLT - PET responses were more significant predictors of overall survival (1 to 2 weeks,  $P = .006$ ; 6 weeks,  $P = .002$ ), compared with the MRI responses ( $P = .060$  for both 6-week and best responses). In univariate and multivariate Cox regression analysis, lack of FLT reduction at 6 weeks was the best predictor of reduced OS, with adjusted hazard ratio = 4.955 ( $p = 0.02$ ). Assuming 50% of subjects are metabolic responders, median survival of 3.4 months in non-responders and two years of follow up, a sample size of N = 22 subjects with follow up PET scans will provide 85% power to detect a hazard ratio of 4.9 using a two-sided logrank test at the 0.0125 significance level.

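### Section 7.3 claims 85% power for a hazard ratio of 4.9, but the two-sided log-rank test it names has about 75–77% with 22 patients

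*Combined protocol and SAP*

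**What the plan says.** The last sentence of Section 7.3 sets out its inputs: "Assuming 50% of subjects are metabolic responders, median survival of 3.4 months in non-responders and two years of follow up". It then concludes that "a sample size of N = 22 subjects with follow up PET scans will provide 85% power to detect a hazard ratio of 4.9". The test behind this claim is specified in the same sentence: "using a two-sided logrank test at the 0.0125 significance level". That level matches Section 7.2 (Primary Endpoint): "Each analysis will be performed at the two sided 0.0125 significance level to adjust for four comparisons".

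Section 7.3 names no formula or software, gives no expected number of deaths, and does not say whether the two years are counted per patient or from the last enrolment. It gives no accrual period either, though Section 5.1 supplies one indirectly: "Eight to ten patients per year will be enrolled, for a total of 30 patients".

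**The concern.** The power statement is about a named test on stated inputs, so it can be checked. Twenty-two patients, about 20 deaths and a hazard ratio near 5 are conditions in which the usual large-sample formulas are unreliable. They are derived for hazard ratios close to 1 and assume that the two groups stay balanced among patients still at risk. With a hazard ratio of 4.9 the non-responders die early, and the later deaths occur among patients who are nearly all responders. Those deaths add little information, yet the formulas count them in full.

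Section 7.3 is the only justification given for the sample size, and Section 1.1 says of the results: "This initial data will be important for design of subsequent clinical trials". A later team that reads a negative comparison here, or reuses the method, would take the risk of missing a hazard ratio of 4.9 to be 15%.

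**Working it through.** **Inputs.** From Section 7.3: N = 22, half responders (11 v 11), non-responder median 3.4 months, hazard ratio 4.9, two-sided 0.0125 (critical value 2.498). From Section 5.1: 30 patients at 8–10 a year, so 30/10 = 3 years to 30/8 = 3.75 years, or 36–45 months. Assumed, because the documents do not say: exponential survival, uniform accrual, no loss to follow-up. The responder median is then 3.4 × 4.9 = 16.66 months.

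**Expected deaths.** With 24 months per patient the death probabilities are 0.992 (non-responders) and 0.632 (responders), so 10.92 + 6.95 = 17.9 deaths. Accrual of 36 or 45 months plus 24 months after the last enrolment gives 19.9 or 20.2.

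**Reproducing 85%.** Schoenfeld's formula is Φ(√(d/4) × ln 4.9 − 2.498), with ln 4.9 = 1.589:

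- 17.9 deaths: 80.5%
- 19.9 deaths: 85.2%
- 20.2 deaths: 85.8%

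The stated figure therefore appears with the Section 5.1 accrual plus 24 months. With exactly 24 months per patient, Schoenfeld does not give it. An exponential log-hazard-ratio formula with separate null and alternative variances does come close there, at 84.6%.

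**Power of the test itself.** The log-rank test was simulated, 200,000 runs per case, and also evaluated by Lakatos's method, which follows the changing balance of the groups at risk. Power in %:

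| Calculation | 24 months each | 36 + 24 | 45 + 24 | All 22 die |
|---|---|---|---|---|
| Schoenfeld | 80.5 | 85.2 | 85.8 | 89.1 |
| Exponential log-HR, variance 1/d₀ + 1/d₁ | 78.1 | 84.8 | 85.4 | 89.1 |
| Freedman | 61.7 | 67.4 | 68.1 | 72.7 |
| Lakatos | 75.1 | 75.8 | 75.8 | 75.9 |
| Simulated log-rank, 11 v 11 | 76.6 | 77.3 | 77.4 | 77.5 |
| Simulated log-rank, random 50% split | 74.2 | 74.9 | 74.7 | 75.1 |

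The first and last columns show the mechanism. Going from 17.9 to 22 deaths raises Schoenfeld's figure by 8.6 points but the simulated power by only 0.9. Extra follow-up cannot close the gap.

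A third reading, two years as total study time with entry throughout, gives about 55%. It does not fit Section 5.1, since only 16–20 patients would enrol in that time.

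**Size of the test.** At 11 v 11 the asymptotic log-rank test rejects 1.8–1.9% of the time under the null, against the nominal 1.25%. Held to a true 1.25%, its power is about 71%. So 75–77% is, if anything, generous.

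**What N = 22 does support at 85%.** At 11 v 11, a hazard ratio of 5.9 with 24 months each gives 85.1%, and 5.8 with accrual plus 24 months gives 85.3–85.5%. With a random split, 6.1–6.2 is needed.

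**The case against.** The strongest reply is that 85% is what conventional formulas return on the protocol's own inputs, so this is an optimistic approximation and not a wrong number. That is fair as a possible account of the figure's origin, but it cannot be confirmed. A one-sided 0.0125 test with 24 months per patient has 84.4% simulated power, so a slip in sidedness would fit as well. Either way, the text attributes 85% to a two-sided log-rank test that does not have it.

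Two further points stand. First, accrual is missing only from Section 7.3, because Section 5.1 supplies it. Second, the inputs may matter more than the approximation. The medians quoted from the source study, 10.8 and 3.4 months, have a ratio of 10.8/3.4 = 3.2. At a hazard ratio of 3.18 the same design has only about 47–48% power. The 3.4-month figure also comes from a study "in patients receiving Bevacizumab and Irinotecan as second line therapy", whereas Section 2.1 says that "the median survivals for newly diagnosed GBM and AA are 50 and 150 weeks, respectively". This is a separate weakness. It does not rescue the 85%, and it means that 75–77% should be read as the power on the stated inputs, not as a forecast.

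The study is repeatedly described as exploratory, and that limits how much weight the point carries.

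**Conclusion.** The concern holds. On the inputs in Section 7.3, the named test has about 75–77% power at 11 v 11 and about 74–75% with a random split: a shortfall of about 8–11 points from the stated 85%. The risk of missing a hazard ratio of 4.9 is about 23–25% per comparison at 11 v 11, which is more than half as large again as the implied 15%.

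This rests on exponential survival, uniform accrual and no loss to follow-up, the usual assumptions behind such a statement. Under them the conclusion does not depend on how the two years are read, since power stays below 78% with every death observed. For scale, about 26 analysable patients (13 v 13, 24 months each) would be needed for 85% at a hazard ratio of 4.9. The statement should be corrected, but data collection and the planned analyses are not affected.

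**What to change.** Replace the closing power sentence of Section 7.3 with wording such as: *For 22 patients split 11 v 11, the asymptotic log-rank test at a nominal two-sided level of 0.0125 has about 75–77% power for a hazard ratio of 4.9 (about 74–75% if the responder split varies by chance) and about 85% for a hazard ratio of about 5.9.* In the same place, name the method, give the accrual period (36–45 months follows from Section 5.1), state the survival assumption, and say whether the two years are fixed per patient or run from the last enrolment.

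Two optional additions would help. Note in Section 7.3 that the 3.4-month median comes from second-line patients. Align the follow-up wording across the document: Section 5.2 treats 24 months from recruitment as a maximum, Appendix A treats 24 months as a minimum, and Section 4.3.1 sets a 12-month minimum after the final scan.

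The cost is a text change and a less favourable stated power. N, the significance level and the analyses do not change.

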## 8. REGULATORY AND REPORTING REQUIREMENTS

The AE reporting time frame for this study with two investigational radiopharmaceuticals is 24 hours post injection of each tracer. This is defined in FDA regulation (see section 8.4.1). Per the approval of IND 76, 843 for [F]FLT on 2/1/07 the following reporting of unexpected fatal or life threatening events, serious adverse events, and serious and unexpected adverse events will occur: (1) Reporting any unexpected fatal or life threatening adverse experience associated with the use of [F]FLT by telephone or fax no later than 7 calendar days after initial receipt of the information. (2) Reporting any adverse experience associated with the use of [F]FLT, that is both serious (SAE) and unexpected in writing no later than 15 calendar days after initial receipt of the information. (3) Submitting annual reports. The reportable events will also be submitted to the IRB using the University of Utah ERICA online system: <https://erica.research.utah.edu/erica/Rooms/DisplayPages/LayoutInitial?Container=com.webbridge.entity.Entity%5BBOID%5B5FD2DA60262617429607E459C0E09D92%5D%5D>

The same reporting process and requirements will be used for [F]Fluciclovine.

The descriptions and grading scales found in the revised NCI Common Terminology Criteria for Adverse Events (CTCAE) version 5.0 with subsequent modifications will be utilized for adverse event reporting (<http://ctep.cancer.gov/reporting/index.html>).

All appropriate treatment areas will have access to a copy of the CTCAE version 5.0 with modifications. A list of adverse events that have occurred or might occur (Reported Adverse Events and Potential Risks) can be found in Section 6 (Methods for Evaluation of Imaging Studies).

### 8.1. Informed Consent

Informed consent will be obtained from all research participants prior to performing any study procedures using the most recent IRB approved version.

## 8.2 Institutional Review

Study will be approved by the Institutional Review Board of University of Utah.

## 8.3 Data and Safety Monitoring Plan

A Data and Safety Monitoring Committee (DSMC) is established at Huntsman Cancer Institute (HCI) and approved by the NCI to assure the well-being of patients enrolled on Investigator Initiated Trials that do not have an outside monitoring review. Roles and responsibilities of the DSMC are set forth in the NCI approved plan. The activities of this committee include a quarterly review of adverse events including SAEs, important medical events, significant revisions or amendments to the protocol, and approval of cohort/dose escalations. If the DSMC and/or the PI have concerns about unexpected safety issues, the study will be stopped and will not be resumed until the issues are resolved. The DSMC also reviews and approves audit reports generated by the Research Compliance Office.

### 8.3.1 Data Reporting

This study will be monitored by the Principal Investigator using the ERICA system. In addition, the study will be monitored by the HCI Data and Safety Monitoring Committee. Cumulative data will be submitted electronically to ERICA, the HCI Data and Safety Monitoring Committee, and the IRB as required.

## 8.4 Adverse Events / Serious Adverse Events

This study will utilize the CTCAE (NCI Common Terminology Criteria for Adverse Events) version 5.0 for AE and SAE reporting. An electronic copy of the CTCAE version 5.0 can be downloaded from: [https://ctep.cancer.gov/protocolDevelopment/electronic\\_applications/etc.htm#etc\\_50](https://ctep.cancer.gov/protocolDevelopment/electronic_applications/etc.htm#etc_50)

### 8.4.1 Adverse Events (AE)

An adverse event is the appearance or worsening of any undesirable sign, symptom, or medical condition occurring after receiving the radioactive tracer(s). For the purposes of this study, the terms toxicity and adverse event are used interchangeably. Medical conditions/diseases present before starting the study are only considered adverse events if they worsen after being injected with the radioactive tracer(s). Abnormal laboratory values or test results constitute adverse events only if they induce clinical signs or symptoms, are considered clinically significant, or require therapy.

Adverse event reporting for studies assessing diagnostic radiopharmaceuticals have different criteria than for therapeutic drugs. The NCI CTEP requires that AE's be reported for up to ten half-lives after the administration of the tracer rounded UP to the nearest whole day. In this instance, the half-life of the F radioisotope is 110 minutes, with ten half-lives equivalent to 18.33 hours. This study will therefore collect adverse events from the time the radiopharmaceutical is administered and 24 hours afterward, even if the event is not considered to be related to the tracer.

The collection of any adverse events will begin when a patient receives their first dose of [F]FLT or [F]Fluciclovine and will end 24 hours after receiving that dose. As there is the potential for each patient to receive up to six scanning visits, each constituting a radioactive tracer to be injected into the patient, the adverse events will be monitored for 24 hours after each injection and subsequent scan. Those adverse events that are not associated with [F]FLT and [F]Fluciclovine that do not require expedited reporting will be reported in the routine manner to the IRB.

The occurrence of adverse events should be sought by non-directive questioning of the patient at each visit or phone contact during the study. Adverse events also may be detected when they are volunteered by the patient during or between visits within the AE reporting period or through physical examination, laboratory tests, or other assessments. As far as possible, each adverse event should be evaluated to determine:

1. The severity grade based on CTCAE v.5 (Grade 1-5).
2. Its relationship to the study radioactive tracer(s) (definite, probably, possible, unlikely, not related)
3. Its duration (start and end dates or if continuing at final exam).
4. Action taken (no action taken; study tracer dosage adjusted/temporarily interrupted; study tracer permanently discontinued due to this adverse event; concomitant medication taken; non-drug therapy given; hospitalization/prolonged hospitalization).
5. Whether it constitutes an SAE.

All adverse events will be treated appropriately. Once an adverse event is detected, it should be followed until its resolution, and assessment should be made at each visit (or more frequently, if necessary) of any changes in severity, the suspected relationship to the study tracer, the interventions required to treat it, and the outcome.

Information about common side effects already known about the tracer is described in the Pharmacology and Safety of [F]FLT and [F]Fluciclovine and Radiation Dosimetry of [F]FLT and [F]Fluciclovine (Section 3). This information will be included in the patient informed consent and will be discussed with the patient during the study as needed.

All adverse events will be immediately recorded in the patient research chart.

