### 5.5.3. Day of Research PET Scan(s)

The patient will have the appropriate IV access placed for radiotracer administration. The patient will then be positioned comfortably on the PET imaging table with the PET head-holder attachment. A CT scan for PET attenuation correction will be acquired using x-ray CT (PET/CT scanner). Dynamic PET scans of each tracer will then be acquired, which requires administration of the PET tracer(s) while the scanner is acquiring in dynamic mode. The details of tracer administration are summarized in Table 4.

Table 4. PET Tracer Administration: Route, Dosing, and Blood Sampling

Tracer	Route	Manner	Injected Dose	Scan Mode
[  F]FLT	IV	~60s push	~10 mCi	Dynamic
[  F]Fluciclovine	IV	~60s push	~10 mCi	Dynamic

Each radiotracer will be prepared by the investigational drug radiochemists in the PET cyclotron facility at HCI on the day of the scanning session. The tracer will be administered to the patient by a physician, nuclear medicine technologist, or trained research personnel in the PET imaging suite. Each tracer administration will be pushed by hand as a manually timed infusion (~60s) as indicated by Table 4, where each infusion is designed to optimize dynamic PET efficacy for that tracer.

Adverse events potentially related to the administration of [F]FLT or [F]Fluciclovine will be recorded at the conclusion of the [F]FLT or [F]Fluciclovine study. (Appendix B: Schedule of Events; Appendix D: [F]FLT Infusion Flow Chart, Appendix G: [F]Fluciclovine Infusion Flow Chart).

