## 5.6. Data Collection

### 5.6.1. Safety Data Recorded During [F]FLT-PET and [F]Fluciclovine-PET Scans

Data collected on visit(s) for [F]FLT-PET and [F]Fluciclovine-PET scanning will be recorded on the [F]FLT or [F]Fluciclovine Protocol flow chart and will include: vital signs (including heart rate, blood pressure, and temperature) recorded just prior to the [F]FLT or [F]Fluciclovine infusion and then after the completion of the [F]FLT and [F]Fluciclovine imaging study. In addition to monitoring the above-mentioned safety parameters, an emergency code cart is located in the PET suite and can be utilized by the PET imaging team, as well as accessed by the code team at the institution should an emergent situation arise.

Additional information to be collected will include:

- Questioning of patient regarding adverse events immediately after each [F]FLT and [F]Fluciclovine administration.
- Patients may be discharged after the completion of the [F]FLT or [F]Fluciclovine imaging procedure if stable and if no adverse events are noted on questioning. Patients will be evaluated for adverse events after the completion of the [F]FLT and [F]Fluciclovine scans.

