## APPENDIX B: Schedule of Events

	Screen	Imaging Session 1		Imaging Session 2		Imaging Session 3	
		[  F]FLT	[  F]Fluciclovine	[  F]FLT	[  F]Fluciclovine	[  F]FLT	[  F]Fluciclovine
Assessment/ Procedures							
Informed Consent	X						
Inclusion/ Exclusion Criteria	X						
Laboratory Monitoring	X 			X 		X 	
Infusion of [  F]FLT		X		X		X	
[  F]FLT PET/CT Imaging		X		X		X	
Infusion of [  F]Fluciclovine			X		X		X
[  F]Fluciclovine PET/CT Imaging			X		X		X
Vital Signs 		X 	X 	X 	X 	X 	X 
AE Assessment		X	X	X	X	X	X
Concomitant Medication		X 		X 		X 	

- Laboratory tests will include: (AST, ALT), bilirubin (total), serum electrolytes, CBC with platelets, prothrombin time, partial thromboplastin time, BUN, and creatinine. Female patients who are not postmenopausal or surgically sterile will undergo a serum pregnancy test prior to each imaging session ([F]FLT and [F]Fluciclovine PET scans). The values for the imaging sessions must be within 4.0 X the upper or lower normal limits (unless clinically not relevant). For those patients receiving coumadin or another anticoagulant the upper limit for prothrombin time or partial thromboplastin time must not exceed 6 times the upper limit of the normal range.
- Laboratory tests from the screening visit will be used if the first [F]FLT imaging session are performed within 28 days of the screening laboratory tests. Labs will be redrawn prior to [F]FLT imaging session 1 if they are outside of the 28 day window prior to the scan.
- Within 96 hours prior to the second [F]FLT imaging session the laboratory assessments will be performed. The values for this assessment must be within 4.0 X the upper or lower normal limits (unless clinically not relevant). For those patients receiving coumadin or another anticoagulant the upper limit for prothrombin time or partial thromboplastin time must not exceed 6 times the upper limit of the normal range.

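### Adverse events are to be collected for 24 hours after each tracer injection, but no contact is scheduled after the end of the scan

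*Combined protocol and SAP*

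**What the plan says.** Section 8.4.1 sets the window: "This study will therefore collect adverse events from the time the radiopharmaceutical is administered and 24 hours afterward", whether or not the event is thought to be related to the tracer. It repeats the commitment for repeated dosing, with up to six injections per patient: "the adverse events will be monitored for 24 hours after each injection and subsequent scan". Section 8.4.2 then requires all serious adverse events in the reporting period to be collected, and all deaths in the window to receive expedited reporting.

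The procedural text sits at the scan visit:

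- Section 5.6.1 lists "Questioning of patient regarding adverse events immediately after each" administration, followed by an evaluation once the scan is complete. It allows discharge after the "imaging procedure if stable and if no adverse events are noted on questioning".
- Section 5.5.3 says that tracer-related events "will be recorded at the conclusion of the" tracer study.
- Appendix B marks its "AE Assessment" row only in the six tracer-imaging columns.
- The flow charts in Appendices C and D have a baseline row and an end-of-study row. The questionnaires in Appendices E and F are tied to an imaging visit and have a date line but no field for a later contact.

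Section 8.4.1 also provides for non-directive questioning at visits or by phone, and for events that patients volunteer between visits. It fixes no time for either.

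**The concern.** A collection window is only as good as the step that asks about it. Here the window runs for 24 hours, but the last question scheduled for a given injection comes before the patient goes home. A non-fatal event that begins that evening, or an admission to another hospital, enters the database only if someone mentions it.

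Three things follow. Safety summaries would carry a 24-hour label although active questioning covered little more than the scan. Staff cannot tell from the schedule whether a next-day call is expected, so practice may differ between patients. And few recorded events could be read as few events occurring. Section 3.1.2 itself makes a similar point about the FLT literature: none of the published papers reviewed for the initial IND specifically said whether safety or toxicity had been assessed.

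**Working it through.** **Inputs**

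- Fluorine-18 half-life: 110 minutes (Section 8.4.1).
- Window: 24 hours, or 1,440 minutes, after each injection (Section 8.4.1).
- Blood sampling: 70 minutes for each tracer (Sections 6.1.3 and 6.2.3), omitted where venous access is inadequate.
- Fluciclovine static images: timed from 70 minutes after injection (Section 6.2.2). This may mean that they start then, so the session could be longer.
- Time T from injection to last questioning: not stated. I assume 60 to 120 minutes.

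**Step 1: the plan's own figure.** 10 × 110 = 1,100 minutes, and 1,100 / 60 = 18.33 hours. This matches "with ten half-lives equivalent to 18.33 hours". Rounded up to whole days it gives 1 day, or 24 hours. The window is derived correctly.

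**Step 2: share of the window after the last scheduled question,** 1 − T/1,440.

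| T (minutes) | Share after last question | Hours remaining |
|---|---|---|
| 60 | 95.8% | 23.0 |
| 70 | 95.1% | 22.8 |
| 90 | 93.75% | 22.5 |
| 120 | 91.7% | 22.0 |

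Rounding up to a whole day is not what drives this. Against the unrounded 1,100 minutes, the share is 1 − 70/1,100 = 93.6% at 70 minutes and 1 − 120/1,100 = 89.1% at 120 minutes.

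**Step 3: whether later visits fill the gap.** The note after Appendix B puts the two tracers on separate days, within one to two weeks of each other.

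- First tracer of a session: the next assessment is the second tracer visit. It may be the next day, or up to about two weeks later.
- Second tracer of the baseline session: the next imaging is one to four weeks after roughly six to eight weeks of chemoradiotherapy (Section 5.5.2), so at least about 6 + 1 = 7 weeks away.
- Last injection: no later imaging visit. For a Group B patient, who has one session of two injections, this is one injection in two.

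**Step 4: effect of a scheduled contact.** With one contact at or after 24 hours, none of the window lies beyond the last scheduled question.

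**The case against.** The best reply is that unscheduled is not the same as unobserved. Section 8.4.1 requires questioning at any visit or phone contact and accepts volunteered reports and findings from examinations or tests. Events are often collected by asking afterwards, and the second tracer visit gives such an occasion for the first injection of each session. The Appendix B row has no timing footnote, so its marks do not forbid a later call. Section 5.5.3 covers only events potentially related to the tracer, so it does not narrow the wider collection in Section 8.4.1. All of this stands. A reader might infer that there is no later contact and that about 95% of the window is unobserved; the documents do not support that. What they show is that later coverage has no set time and, for the last injection, no imaging visit to prompt it.

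A reader might also infer that the team has no way to learn of a death or a serious event. That is not so. Overall survival is the primary endpoint, patients are followed for at least 12 months after last imaging (Section 4.3.1), and the eligibility checklist covers record review for at least 24 months. A death would surface, and a hospital admission might, though possibly late.

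Nor does the plan define a 24-hour event rate that would come out wrong. Reporting is by individual event, quarterly committee review and annual IND summary.

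Finally, expected harm is low. Table 1 lists reactions in 12 of 1,153 fluciclovine subjects (about 1%), all mild, and Section 9.1.2 reports none for FLT at this dosage. This limits the importance of the point but does not remove the mismatch.

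**Conclusion.** The point holds as a gap between a stated window and the scheduled means of observing it. For an assumed 60 to 120 minutes from injection to last questioning, about 92% to 96% of each 24-hour window has no scheduled active ascertainment. The 70 minutes is a blood-sampling and image time, not a stated scan length, so the share should be quoted as a range. It is a share of clock time and does not estimate the proportion of events missed.

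The consequence is that non-fatal events, serious ones included, may be missed or reported late. The primary survival analysis is unaffected. The correction is worth making because it is cheap and the commitment in Section 8.4.1 is explicit.

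A related inconsistency bears on the timing of any contact. Section 3.1.4 sets a 28-day safety reporting window for fluciclovine, while the opening of Section 8 and Section 8.4.1 use 24 hours for both tracers. These passages must be reconciled; the documents do not explain the difference.

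**What to change.** First reconcile Section 3.1.4 with Sections 8 and 8.4.1, so that one stated window applies to each tracer. Then take one of two routes.

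1. **Schedule the contact.** Add to Section 5.6.1 and Appendix B one brief adverse-event contact for each injection, at or after the close of the stated window. It can be a call by the existing coordinator, or a visit where one already falls then. Use the Appendix E or F questionnaire with an open question about new symptoms or hospital care, and add a contact date and time field to both forms.
2. **State the limit.** If no contact is intended, say in Section 8.4.1 and in safety reports that active questioning ends at scan completion and that later events are captured passively.

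The first route costs a schedule row, a form field and up to six short calls per patient. Across 30 patients the ceiling is 6 × 30 = 180 calls, and fewer in practice because Group B patients have two injections. More background symptoms unrelated to the tracers will be recorded. The second route costs only wording, but leaves ascertainment as it is. Neither changes eligibility, dosing, imaging or the primary analysis.
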